6.5. Screening and Preoperative Baseline Evaluation

One to two months before DBS implant surgery (with 1 month defined as 30 days \pm 3 days), participants will complete physical and neurological screening examinations and complete laboratory studies to ensure study eligibility and suitability for surgery. A screen failure is defined as a potential participant who has been consented for screening but is not enrolled for randomization and implantation. A screen failure does not meet all inclusion criteria and/or has answered or tested affirmatively to any exclusion criteria. A potential participant may also fail screening if they are deemed unsuitable for participation based on the clinical judgment of the sponsor investigator. We estimate the screen failure rate to be 3:1, which is based on efficiently pre-screening interested participants, and extensive team review of each case prior to screening.

Participants will also undergo pre-operative multi-dimensional baseline assessment using a battery of cognitive (e.g., attention, memory, information processing speed, executive functions), psychological health (e.g., depression, anxiety) functional status (e.g., employment level) and quality of life (e.g., satisfaction with life) measures (see *Description of Outcome Assessments* below). A structured interview will also be conducted to obtain additional background information and determine pre-injury levels of academic, vocational and social function. These evaluations can be done either on a single day or on multiple days.

6.6. Inpatient Hospital Stay

Following completion of the preoperative baseline evaluation, participants will be admitted for surgical implantation of the DBS system. All patients will receive one DBS lead in each side of the diencephalon. Both leads will be connected to a single pulse generator that may be implanted on the right or left side of the chest. The procedures may be performed on the same day or staged. The surgical procedures are discussed in more detail below.

6.6.1. Stage I: Bilateral DBS Lead Implantation

Patients will undergo implantation in a fashion similar to that routinely performed by the investigators for movement disorders (Bronte-Stewart, Louie, Batya, & Henderson, 2010 [3]; [name] et al., 2006 [15]). We anticipate that targeting will be simpler in the present study than in our prior experience ([name] et al., 2007 [22]) because patients in the present population are expected to have less post-traumatic gross anatomical deformities of the cerebrum and diencephalon (see [Figure 3](#)). Surgical planning will be performed prior to surgery based on preoperative volumetric MR images acquired with and without contrast, unless there is a clinical contraindication to the use of contrast ([Figure 4](#) below).

Figure 3: Bilateral DBS, targeting the central thalamic region. In this example, the DBS lead has 1.5 mm height contacts, separated by 1.5 mm gaps. The ventral-most contact was targeted at the central lateral nucleus of the thalamus.

[figure not shown]
[figure not shown]

Figure 4: Thalamic nuclei visualized at 7T (left), with corresponding segmentations (right) based on the Morel thalamic atlas (Tourdias, Saranathan, Levesque, Su, & Rutt, 2013 [32]). The central lateral nucleus is highlighted in orange.

One or more days prior to surgery, five stainless steel fiducial markers will be implanted in the skull through small stab incisions under local anesthesia in the neurosurgery outpatient clinic

(Holloway et al. 2005 [12]). A high-resolution volumetric CT scan will be obtained and these images will be imported into the surgical planning station and fused with the previously obtained MRI images, and the final target location determined. On the day of surgery, the patient will be positioned in a custom head cradle. The patient's anatomy will be registered to the neuronavigational system by touching each fiducial marker with a passive planar registration probe equipped with reflective spheres, which can be tracked by the cameras of the surgical navigation unit. Entry points will be marked on the scalp and the patient will be prepared and draped in a sterile fashion. After burr-hole placement, high-impact plastic towers will be attached to the skull bilaterally with 3 titanium bone screws. A sterile reference arc will be fastened to the base of the platform to allow real-time tracking for maximum accuracy. Each fiducial marker will be touched through the drape to perform registration again. Alignment of the trajectory will be accomplished by adjusting the frameless device platform to orient the trajectory to the planned target, using the guidance view of the target provided by the planning software.

Implantation will be guided either by intraoperative imaging (O-arm or MRI) or by microelectrode recording and intraoperative macrostimulation via the DBS leads. Image-guided procedures will be performed under general anesthesia. Microelectrode-guided procedures will be performed under conscious sedation, titrated according to the judgement of the anesthesiology team. In either case, routine procedures for DBS placement will be used. In a recent meta-analysis, no significant difference was found between the two techniques with regard to targeting accuracy and symptom reduction (Ho et al. *Mov Disord* 2017). Based on the results from the first 5 patients in this study, there does not appear to be a unique neurophysiological signal associated with the CL nucleus. In addition, intraoperative stimulation has not caused side effects that proved informative with relation to the eventual postoperative lead location. Therefore, the final patient in the study will be implanted using image guidance, which we believe will result in equivalent or improved accuracy.

Once the final location for the DBS lead is selected, it will be anchored to the skull in the routine fashion and the surgical sites closed under sedation. The procedure will then be repeated on the opposite side. Following surgery, the patient will be admitted for observation under routine neurosurgical care for intracranial surgery. The investigators will attempt to implant both sides in the same surgical procedure. However, if the patient is tired or, if in the opinion of the investigators there is added risk to completing the implantation of the second side in the same day, the investigator can make the decision to stop the surgery and implant the second side in a separate date, no more than 60 days after implantation of the first side. Because this is routinely done in surgery for movement disorders we will not consider staging of the DBS lead implants to be a deviation of the protocol. At least one CT scan will be done postoperatively during the hospital admission to verify lead location and rule out intracranial hemorrhage.

6.6.2. Stage II

Implantable pulse generator (IPG) implantation and connection to the DBS leads. This is a routine procedure that will be performed under general anesthesia on the same day, following bilateral DBS lead implant. The pulse generator (Model 37601 PC, Medtronic, Inc., Minneapolis, MN) will be implanted on the right or left chest and connected to the DBS leads. Under general anesthesia and with standard surgical technique for DBS, the skin over the distal tip of the leads (protected by a temporary connector) will be opened and the connector externalized and discarded. An approximately 7-10 cm incision will be made in the

infraclavicular region and a pocket fashioned for the pulse generator. A tunneling tool will be used to create a subcutaneous tunnel connecting the infraclavicular subcutaneous pocket to the scalp incision where the lead is externalized. The extension wires will be passed with the tunneling tool. The extension wires will then be connected to the DBS leads and to the pulse generator. Medical adhesive may be used to insure a tight seal and improve signal quality. The incisions will then be approximated with standard surgical technique.

6.7. Post-Surgical Washout Phase

Participants will enter the washout phase following hospital discharge. The length of the baseline will be staggered for each participant pair. The purpose of this phase is twofold: (1) to provide a 30-day surgical washout for resolution of any transient physiological or behavioral effects of surgery and (2) to detect the temporal onset of the stimulation effects for each subject, should these occur at the time of stimulation titration onset. At the end of the surgical washout period, the multidimensional outcome assessment battery that was administered during the pre-surgical baseline phase will be repeated to assess for any changes in function before CT-DBS is switched on (see *Description of Outcome Assessments* below). A CT scan will be performed on day 65 to assess the final lead location, after any post-surgical changes have been allowed to resolve.

6.8. DBS Stimulation Titration/Optimization

On completion of the postsurgical washout phase (beginning day 66, 80, or 94, depending on cohort), DBS will be turned on for the first time to initiate the stimulation titration phase. During this phase, which will last 14 days for all participants, an array of stimulation parameters will be assessed to optimize the settings that will be used during the treatment phase. See [Appendix 1](#) to this protocol for the device programming SOP.

6.9. Unblinded Treatment Phase

After DBS titration/optimization is complete, participants will enter the unblinded 90-day treatment phase during which DBS will remain on for 12 hours per day. At the end of the 90-day treatment phase, participants will undergo re-assessment on the multi-dimensional outcome assessment battery. Electrophysiologic measures will also be sampled on day 139 (± 3 days), 153 (± 3 days), or 167 (± 3 days), respectively, to compare performance before and after treatment.

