6.3. Randomization to Multiple Baseline Condition and Treatment Withdrawal

Following study enrollment, participants will be randomly assigned to 1 of 3 baseline conditions lasting 30, 44, or 58 days. Two participants will be assigned per condition. The staggered baseline schedule will enable assessment of CT-DBS effects within individual subjects and across subject pairs. Each participant will also be randomly assigned to a treatment withdrawal or continuation condition. Neither the investigator nor the participant will have knowledge or be apprised as to whether DBS is on or off during this period. For participants assigned to the treatment withdrawal condition, DBS will be switched off for 21 days (on days 170, 184, and 198 for cohorts 1-3, respectively) immediately after completing the 90-day unblinded treatment phase. Participants randomized to the continuation condition will continue to receive stimulation 12 hours per day over the same 21-day period. Upon conclusion of the 21-day treatment withdrawal phase, participants will undergo a final re-assessment on the multi-dimensional outcome assessment battery and on the electrophysiologic measures (on day 191, 205, or 219, depending on cohort). Currently there are no known safety issues related to withdrawing stimulation. The purpose of this follow-up visit is to determine if there is evidence of loss of effect in those assigned to the treatment withdrawal condition, and to evaluate the influence of

intervening factors on the effectiveness of DBS. The trial will be considered complete at the end of the treatment withdrawal phase.

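### Section 6.9 dates its before-and-after electrophysiology on treatment day 60 of 90, and the protocol gives two different ends of study

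*Combined protocol and SAP*

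**What the plan says.** **Schedule.** Section 6.8 turns stimulation on for a 14-day titration phase "beginning day 66, 80, or 94, depending on cohort". Section 6.9 follows this with 90 days of unblinded treatment and places the outcome battery at their end. For the withdrawal condition, 6.3 states that "DBS will be switched off for 21 days (on days 170, 184, and 198 for cohorts 1-3, respectively" and puts this "immediately after completing the 90-day unblinded treatment phase". The final re-assessment in 6.3 covers the battery and the "electrophysiologic measures (on day 191, 205, or 219, depending on cohort".

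**Electrophysiology.** Section 6.9 adds "Electrophysiologic measures will also be sampled on day 139" (153 and 167 for the other cohorts, all ±3 days) in order "to compare performance before and after treatment". Section 7.7.1 places the first EEG on the day of surgical admission and says that recordings are made several times after implantation, without further dates. No section defines day 1.

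**End of study.** Sections 6 and 6.3 both close the study when the withdrawal phase ends. The synopsis gives a total of 12 to 14 months and lists the 6-month open-label follow-up among the main phases. Section 6.11 starts that follow-up when unblinded treatment ends, with visits at months 3 and 6.

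**The concern.** A comparison of performance before and after treatment needs a recording at or after the end of treatment. If the 6.9 dates lie inside the treatment phase, a team following the protocol would take a mid-treatment recording and report it as post-treatment. The later session in 6.3 cannot fill the gap: by then a participant has had either 21 days without stimulation or 21 further days with it.

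The second issue is the observation period for safety. Section 9.1 defines adverse events as occurring during the investigation, 9.5.4 limits death reporting to the course of the study, and section 10 runs committee reviews throughout it. With two ends of study, it is unclear whether these provisions reach the 6-month follow-up.

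**Working it through.** **Inputs.** Titration start 66/80/94 and length 14 days (6.8); treatment length 90 days and electrophysiology days 139/153/167 ±3 (6.9); switch-off 170/184/198 and final assessment 191/205/219 (6.3).

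**Step 1: reproduce the protocol's own dates.** First treatment day = titration start + 14. Last treatment day = first + 89. Switch-off = last + 1. Final assessment = switch-off + 21.

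| Cohort | Treatment days | Switch-off: computed / stated | Final assessment: computed / stated |
|---|---|---|---|
| 1 | 80–169 | 170 / 170 | 191 / 191 |
| 2 | 94–183 | 184 / 184 | 205 / 205 |
| 3 | 108–197 | 198 / 198 | 219 / 219 |

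All six stated dates are reproduced. Two further figures fit the same count. The CT scan on day 65 (6.7) is the day before cohort 1 is switched on. Under 6.3, "participants will be randomly assigned to 1 of 3 baseline conditions lasting 30, 44, or 58 days", and subtracting these lengths from the titration starts gives one common day: 66 − 30 = 80 − 44 = 94 − 58 = 36.

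**Step 2: place the electrophysiology dates.** Treatment day = date − first treatment day + 1.

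- Cohort 1: 139 − 80 + 1 = 60
- Cohort 2: 153 − 94 + 1 = 60
- Cohort 3: 167 − 108 + 1 = 60

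With ±3 days the range is treatment day 57–63. The last treatment day is 169 − 139 = 30 days later (27–33 over the window), and the same holds in cohorts 2 and 3. No date within the window reaches the end of treatment.

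**Step 3: end of study.** At 30.44 days per month, the withdrawal phase ends at 191/30.44 = 6.3, 205/30.44 = 6.7 and 219/30.44 = 7.2 months. Section 6 allows 30 to 60 presurgical days. Adding 30 more gives 221/30.44 = 7.3 to 249/30.44 = 8.2 months, still short of 12. Adding a 6-month follow-up (taken as 183 days) after withdrawal gives (191 + 183)/30.44 = 12.3 to (219 + 183)/30.44 = 13.2 months. The synopsis duration therefore appears to include the follow-up that sections 6 and 6.3 leave outside the study.

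**Step 4: start of follow-up.** For cohort 1, unblinded treatment ends on day 169 and the last blinded day is 190. The two possible starting points differ by 190 − 169 = 21 days.

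**The case against.** **The dates may use another day count.** Section 6.5 refers to a presurgical month, "with 1 month defined as 30 days" with a tolerance of 3 days. Adding 30 to the 6.9 dates gives 169/183/197, exactly treatment day 90. From this a reader might infer that the session was meant for the last treatment day, and that its window then runs past switch-off into the double-blind phase (166–172 in cohort 1, with 3 of 7 days on or after day 170). The documents do not support that as a finding. No section states such an offset, and 6.5 defines the month only for timing the screening work before surgery. Even with the offset, the nominal dates precede switch-off and only the upper tolerance crosses it. The result also depends on the offset chosen: 27 days puts no window day past treatment, 33 puts six of seven past it, and 35 (counting from the common day 36 above) puts the nominal date after switch-off. What stands is that day 1 is undefined, so the intended date cannot be recovered from the text.

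**A mid-treatment session may have been intended.** Section 7.7.1 also plans device power samples every ten minutes over 2 months, downloaded at visits, and treatment day 60 is about two months in. The purpose clause could loosely mean before and after treatment began. This is possible, but the text does not link the two, and the clause follows directly on the end-of-treatment battery. On this reading the wording still needs correcting.

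**Little depends on it.** Electrophysiology is exploratory (7.7), section 11 specifies no contrast for it, and 7.7.1 does not rule out further recordings. This stands, and it limits the point.

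**The end of study is only wording.** A reader might infer that safety events in follow-up would go unreported. That goes too far. Section 11 summarizes follow-up safety data, 9.5.2 sets no such limit on reporting unanticipated device effects, and section 10 has serious events reviewed as they occur. The study also keeps running for earlier participants while later ones are still in it. The ambiguity is partial and falls chiefly on the last participants.

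**Conclusion.** The point holds. On the only day count that the protocol supports, the 6.9 electrophysiology falls on treatment day 60 of 90 (57–63) in all three cohorts. That contradicts its stated purpose, and no session is dated at the end of treatment. This rests on the stated phase lengths running consecutively, which the six reproduced dates confirm. Whether the dates or the purpose clause is at fault cannot be settled from the documents. The consequence is confined to exploratory data; the primary outcome and its timing are unaffected.

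The two ends of study are a separate conflict in wording, not a counting error: 6.3–7.2 months (7.3–8.2 with 30 more presurgical days) against 12–14. The follow-up start in 6.11 is a minor inconsistency. It coincides with the start of the 21-day double-blind phase, whereas the synopsis lists follow-up after that phase, by order only and without a date. The effect is a 21-day shift in two visits.

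**What to change.** 1. Define day 1 and reconcile 6.9 with 6.3 and 6.8 on it. Either date the after-treatment session at the end of the 90 days, with a window that closes before switch-off, or keep 139/153/167, call it a mid-treatment sample and delete the before-and-after purpose.
2. In the analysis, report every recorded session by actual treatment day and by stimulation status at recording. Do not present recordings near treatment day 60, or any made after switch-off, as end-of-treatment.
3. State one end of study across sections 6 and 6.3 and the synopsis. Say explicitly that adverse event tabulation, death reporting and committee review cover the follow-up period.
4. Reconcile the follow-up start in 6.11 with the double-blind phase and the synopsis order.

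**Cost.** These are short text changes with no added procedure. Section 13.5 requires FDA and IRB approval if they are judged substantive. Section 6.6.1 already reports results from the first five of six patients, so re-dating can help few sessions. For recordings already made, item 2 is the effective remedy and needs only the recording dates and the stimulation status at each.

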6.10. DBS Stimulation Long-term Continuation

If ongoing benefits for the subject are determined by the patient and the team, the patient will continue long-term DBS. Decisions about the presence of benefit are expected to be guided by evidence of causal influence of DBS on changes in neuropsychological functions that covary with clinically meaningful outcomes on performance measures or quality of life indices. After the initial battery expires, a rechargeable replacement will be available for individuals who will continue with stimulation.

6.11. Six Month Open Label Follow-Up Period

There will be a 6-month follow-up period at the end of the unblinded treatment phase. There will be two visits during this period with the visits occurring at months three and six. The month three follow up visit will be to assess general health, quality of life and to monitor battery supply

of the device. The six month follow up visit will be to assess general health, quality of life, neuropsychological status and to monitor battery supply of the device.

6.12. Unscheduled Visits:

Participants may have visits in between their regularly scheduled study visits if the sponsor-investigator deems necessary.

7. DESCRIPTION OF OUTCOME ASSESSMENTS

7.1. Measures of Cognition

- **Trail Making Test (Primary Outcome Measure) {Army Individual Test Battery, 1944, Manual of directions and scoring}**. The TMT is a measure of attention, speed, and mental flexibility. It also tests spatial organization, visual pursuits, recall, and recognition. Part A requires the individual to draw lines to connect 25 encircled numbers distributed on a page. Part A tests visual scanning, numeric sequencing, and visuomotor speed. Part B is similar except the person must alternate between numbers and letters and is believed to be more difficult and takes longer to complete. Part B tests cognitive demands including visual motor and visual spatial abilities and mental flexibility. Both sections are timed and the score represents the amount of time required to complete the task.
- **Ruff 2 & 7 (Ruff, 1992, The Ruff 2 and 7 Selective Attention Test: a neuropsychological application)**. The Ruff 2 & 7 Test was developed to measure two aspects of visual attention: sustained attention (ability to maintain consistent performance level over time) and selective attention (ability to select relevant stimuli while ignoring distractors). The test consists of a series of 20 trials of a visual search and cancellation task. The respondent detects and marks through all occurrences of the two target digits: “2” and “7.” In the 10 Automatic Detection trials, the target digits are embedded among alphabetical letters that serve as distractors. In the 10 Controlled Search trials, the target digits are embedded among other numbers that serve as distractors. Correct hits and errors are counted for each trial and serve as the basis for scoring the test. Speed scores reflect the total number of correctly identified targets (hits). Accuracy scores evaluate the number of targets identified in relation to the number of possible targets.

7.2. Physical Symptoms (self-report)

- **Rivermead Post-Concussion Symptom Questionnaire (RPQ) {King, 1995, The Rivermead Post Concussion Symptoms Questionnaire: a measure of symptoms commonly experienced after head injury and its reliability}**. The Rivermead PCS Questionnaire (RPQ) was originally developed as a measure of severity of symptoms following mild TBI. It consists of 16 post-concussion symptoms including headaches, dizziness, nausea/vomiting, noise sensitivity, sleep disturbance, fatigue, irritability, feeling depressed/tearful, feeling frustrated/ impatient, forgetfulness, poor concentration, taking longer to think, blurred vision, light sensitivity, double vision and restlessness. In the original version of the RPQ, participants are asked to rate the

degree (on a scale of 0 to 4) to which a particular symptom has been absent or a mild, moderate or severe problem over the previous 24 hours compared with premorbid levels.

